**First and Last Exercise Session - Upon Arrival:**

Participants will be advised to park near the Education Complex and either use UCF parking pass (if they already have one) or will pay to park using a kiosk. They will be instructed to enter the Education Complex doors facing the A and I parking garages/parking lot.

Only 1 participant will be scheduled for a 1.5-2-hour period, as the data collection could take up to 2 hours. Reminders about collection will be sent on the day before and if applicable (e.g., afternoon collection) on the same morning.

The reminder emails will provide an opportunity for participants to confirm or reschedule.

Subjects will report to the Rehabilitation, Athletic assessment Dynamic, Imaging (READY) laboratory in the Institute of Exercise Physiology and Rehabilitation Science for the beginning of the study procedures and first and last exercise sessions.

**Consent and Screening: (~15-20min)**

Informed consent will be obtained for all subjects as outlined in the consent process selection for this protocol. The informed consent document will ask the participant to self-report any exclusion criteria that is listed. After obtaining informed consent, subjects will fill out a questionnaire asking previous and current health history (health history form). Demographic information will also be collected at this time, including, age, sex, height, and weight (basic demographic form) . Participants will also complete questionnaires asking about their low back pain (NumericPainRatingScale\_Question), disability (ODI2.1a\_QuestionnairesRCTLBP), credibility and exercise expectancy (CEQ\_questionnairesRCTLBP), Pain Catastrophizing questionnaire (PCS\_QuestionnairesRCTLBP) and fear avoidance beliefs (FABQ\_QuestionnairesRCTLBP). The remaining study procedures will begin immediately after eligibility determination or subjects can return at another date to complete the remainder of the study procedures. Consent, questionnaires, and surveys will be collected using REDCap.

**Exercise familiarization (Up to ~10 min)**

The PBP, TESP, FESP, dead bug, and bird dog will be demonstrated by the researcher. The researcher will demonstrate and teach the participants how the exercises are expected to be performed. The exercises are pictured below.

**Dynamic Ultrasound setup and exercise completion (up to ~45 min)**

The ultrasound transducer will be placed 10cm from the umbilicus over the right lateral abdominal wall with the thoracolumbar fascia visible on the ultrasound screen. The transducer will be secured with a nylon belt and foam block.

- 3 images of the PBP static position and 3 images of the PBP starting position will be obtained.
- 3 images of the TESP static position and 3 images of the TESP starting position will be obtained.
- 3 images of the FESP static position and 3 images of the FESP starting position will be obtained.

- 3 images of the dead bug static position and 3 images of the dead bug starting position will be obtained
- 3 images of the bird dog static position and 3 images of the bird dog starting position will be obtained.

A total of 30 images for the right abdominal wall will be obtained. The ultrasound transducer will then be moved to the participants left lateral abdominal wall and pictures will be repeated.

Upon the collection of 60 images, the ultrasound transducer will be taken off the participant and they will complete the PBP, TESP, FESP, dead bug and bird dog until discontinuation. The TESP and FESP will be completed bilaterally so the left and right elbow will be placed on the ground.

[figure not shown]
PBP static position and starting position:

TESP static position and starting position:

FESP static position and starting position:

Dead bug static position and starting position:

Bird dog static position and starting position:

[figure not shown]

**Ultrasound, transducer, nylon belt and foam block to secure to lateral abdominal wall.**

### **Protocol Description and Participant Reporting (*up to ~ 20 min*)**

Upon completion of the exercises, participants will be explained the weekly exercise form that each participant in both groups will be completing and reporting back to the researcher via REDCap. The form will include exercise duration and an exercise form rating (Weekly Exercise Form). This is also the time weekly meetings will be discussed. We will get in touch with the participants weekly either using zoom (video call) or by email to answer any comments or concerns

regarding the exercise completion. The participants email will be provided to the principal investigator when they email showing interest in the study or listed on the “basicdemographic\_questionnaire”. Additionally, this is the time when the exercise videos are emailed to the participants in the leaderboard group. The email will contain private YouTube links only accessible via the link provided to them (ExerciseVideoLinksEmail). The weekly exercise form is described below.

### **Weekly Exercise Completion Form**

A blank weekly exercise form will provide to the participants via email during the first exercise session and another blank form can be provided if participants misplace or delete the form. The participants will then be emailed a link via REDCap to upload their weekly exercise form once the week is over.

Week 1	Repetitions	Day 1 Time	Day 2 Time	Day 3 time
PBP	Rep 1			
	Rep 2			
	Rep 3			
TESP (R)	Rep 1			

	Rep 2			
	Rep 3			
TESP (L)	Rep 1			
	Rep 2			
	Rep 3			
FESP (R)	Rep 1			
	Rep 2			
	Rep 3			
FESP (L)	Rep 1			
	Rep 2			
	Rep 3			
Dead bug	Rep 1			
	Rep 2			
	Rep 3			
Bird dog	Rep 1			
	Rep 2			
	Rep 3			

### Leaderboard Distribution

Upon receiving the exercise forms, a leaderboard will be constructed and sent out over that exercise week's following weekend to the individuals in the leaderboard group. The de-identified leaderboard for week 1 – week 2 will contain each participant's average exercise durations of the 7 exercises. Weeks 2 – weeks 6 will contain each participants average session times and will be stratified into 3 categories. The weekly leaderboard contains reference times from healthy individuals who have completed the same exercises until discontinuation. The reference values come from a previous data collection by the principal researcher and are from a different study population. Healthy, active participants

completed the same exercises in this study until discontinuation.

### Weekly Leaderboard

Exercise	Avg Day 1 time (s)	Avg Day 2 Time (s)	Avg Day 3 Time (s)	Avg Time (s)	Top Time (s)	Reference time (s)
						
PBP						95
TESP (R)						59
TESP (L)						59
FESP (R)						43
FESP (L)						43
Dead bug						100
Bird dog						135

- All questionnaires and surveys that will be collected from the subjects are listed below.

#### Patient Reported Outcomes (Subjective Questionnaires)

Each group will be completing the ODI, NPRS, CEQ, FABQ, PCS, Hooper and MacKinnon and Pain Catastrophizing questionnaire at baseline, after 3 weeks and after 6 weeks.

The SUS, EARS will be completed after 3 weeks and 6 weeks.

The GROC will be completed after the 6th week. All questionnaires will be completed again through REDCap at the 12, 18, and 24-month time points.

Lateral abdominal wall muscle thickness will be collected during the baseline session and during the last exercise session of the 6th week.

**6.4 Data collected during the study will include the ODI, NPRS, CEQ, FABQ, Hooper and MacKinnon and PCS questionnaire at baseline, after 3 weeks and after 6 weeks. The SUS, EARS will be completed at 3 weeks and 6 weeks. The GROC will be completed after the 6th week. All questionnaires will be**

completed again through emails notification for participants to complete through REDCap.

6.5 All questionnaires will be completed again through REDCap at the 12, 18, and 24-month time points.

6.6 N/A

## 7.0 Data and Specimen Banking\*

- 7.1 Ultrasound data will be stored on password protected lab computer for measurement. All data will be de-identified at all stages of collection and analysis. There will be a separate file that includes the name of a participant and participant number that will be stored separately. This file will also be destroyed at least 5 years after the study closure (ParticipantIdentifierDoc). De-identified data will be stored until study closure, then will be maintained on password protected lab computer and stored for at least 5 years after study closure, then destroyed. All questionnaire information will be recorded and kept through REDCap, which requires a UCF login with NID and password. Only members of the study team will have access to the REDCap forms and data associated with this protocol.
- 7.2 The data to be stored with each participant will include the ultrasound images, weekly exercise forms, questionnaires.
- 7.3 Data will be stored and maintained through analysis by the study team and will not be released for any reason.

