## Background\*

Non-specific low back pain (NSLBP) can be defined as low back pain with the absence of a known cause. NSLBP diagnoses are concluded when all other pathologies (specific spinal pathology and radicular syndrome) are excluded. In the primary care setting, 90-95% of all low back cases are non-specific. Individuals of all ages experience NSLBP and are affected at a societal level and personal level. Recent recommendations to decrease low back pain include exercise interventions such as trunk strengthening and endurance, trunk muscle activation, aerobic exercise and multimodal interventions. Other guidelines recommend maintaining a physically active lifestyle. In many cases, maintaining a physically active lifestyle requires exercises to be completed at home via prescribed home exercise programs. In order for the efficacy of the home exercise program to be achieved, consistent exercise adherence must occur. Individuals who adhere to their exercise programs have a greater increase in physical function compared with those who have a lack of adherence. Unfortunately, up to 70% of individuals who suffer from chronic low back pain do not adhere to prescribed home exercise.

The lateral abdominal wall is commonly evaluated in individuals that experience NSLBP. The transverse abdominis, internal oblique and external oblique create the lateral abdominal wall. In individuals with NSLBP, the onset of activity of the deep abdominal muscles is delayed. The use of ultrasound imaging can measure the onset of muscle activation as well as muscle thickness of the lateral abdominal wall. Ultrasound imaging is a non-invasive method to visualize and measure muscle thickness. Images can be

produced during static (non-moving) and functional (moving) positions, demonstrating the change in muscle thickness during rest and during movement. Muscle thickness can be obtained during brightness-mode (B-mode) and Motion-mode (M-mode) by measuring the distance between fascial borders (outward tissue layer of the muscle). M-mode ultrasound is unique as it can also detect the onset of muscle activation. Ultrasound imaging can be implemented to understand trunk strengthening, endurance as well as trunk activation to complement the previous recommended guidelines for decreasing low back pain.

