## **17.0 Data Management\* and Confidentiality**

17.1 For this study, the endpoint is defined as based on previous research regarding home exercise and disability with low back pain we determine that 40 participants (20 in each group) will be necessary, alpha set *a priori* to .05. 40 participants include a 15% attrition rate. Descriptive statistics will be used for age, height, mass. Mean differences, confidence intervals and effect sizes will be used to analyze questionnaires. An activation ratio will be used for the lateral abdominal wall measurements. The static positioning measuring will be used as the numerator and the exercise starting position will be used at the denominator to calculate a ratio.

17.2 All computers storing electronic data will be password protected and only study team members will have access to the passwords. Computers will always remain behind locked doors when not supervised by study team members. All external hard drives used to back up storage will be password protected. Only study team members will have access to these passwords. These passwords will be changed frequently and will be changed immediately if compromised at any point in time.

Participant numbers will be generated by using the IRB # and will be assigned a number (i.e. IRB#12345\_001) as they are enrolled in the study. This number will be utilized in place of any other identifier for the remainder of the study.

Identifiers with de-identified coding will be stored electronically on Redcap and will be deleted after a minimum of 5 years from the time the study closes.

17.3 To ensure quality control of collected data, the 7 exercises performed by participants at their home setting will be demonstrated and taught during the first exercise session with the researcher. Weekly video calls through zoom and emails will be conducted to answer any comments or concerns regarding the exercise completion. We will get in touch with the participants weekly either using zoom (video call) or by email to answer any comments or concerns regarding the exercise completion. The participants email will be provided to the principal investigator when they email showing interest in the study. The leaderboard group will have on demand video that can be accessed at any time and the control take-home packet group will have a packet with pictures and descriptions of the exercises.

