## **25.0 Resources Available**

25.1 Due to the number of individuals in the university area and surrounding East Orlando community, recruiting, and enrolling 40 healthy subjects within a 4-month timeframe is very feasible. Out of the number of students, faculty, and staff on the main campus in general, we do not foresee an issue with recruitment.

The PI will be the primary contributor in conducting and completing the research.

The Rehabilitation Athletic assessment & Dynamic Imaging Laboratory is located in the Education Complex on the first floor in Room 174. It is a 7x11 foot space equipped with a GE NextGen Logiq e ultrasound unit, Delsys Trigno Avanti Electromyography+Inertial Measurement Unit+Biofeedback System, hand-held dynamometer, digital inclinometer, adjustable high/low treatment table, and rehabilitation and exercise equipment.

There is an automated external defibrillator (AED) located just outside of the READY Lab in the hallway leading to Room 174 and a first aid kit for any small wounds. The PI is also a certified and licensed Athletic Trainer in the state of Florida, as well an American Red Cross Certified Professional Rescuer in CPR/AED and First Aid. We are also located near Student Health and CAPS, if the subject happens to be a UCF student, and study team members are also trained to call 911 in case

of any emergency. Any events that would result in an emergency would be reported to the IRB appropriately. All study team members have thoroughly read and studied the protocol and are up to date on all appropriate training. They have met and discussed with the PI their role and clearly described and agreed to that designated in the protocol. They were given time to answer questions to insure they had time to fully understand or clear up any misunderstanding prior to contact with any subjects or commencement of the protocol.

N/A

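### The plan states no provision to mask group or visit when ultrasound thickness, a secondary outcome, is measured from stored images

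*Combined protocol and SAP*

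**What the plan says.** Change in lateral abdominal wall thickness is a secondary objective (Study Summary). The Objectives section states a directional hypothesis: more activation in the gamified arm.

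- **Reading.** Images are taken at baseline and at the last session of week 6 (Patient Reported Outcomes). Section 7.1: "Ultrasound data will be stored on password protected lab computer for measurement". The Background section says thickness is obtained "by measuring the distance between fascial borders". Section 17.1 turns the readings into a ratio, static position over exercise starting position.
- **Protection of the images.** Section 7.1: "All data will be de-identified at all stages of collection and analysis", and "There will be a separate file that includes the name of a participant and participant number that will be stored separately". Section 17.2 gives each person a number on enrolment and adds: "This number will be utilized in place of any other identifier for the remainder of the study". Section 17.4 repeats that the ultrasound measurements are de-identified.
- **People.** Section 19.1 calls the study team small. Section 25.1: "The PI will be the primary contributor in conducting and completing the research". Section 7.3 has the study team keep the data through analysis. The study's researchers teach the exercises, contact participants weekly, email videos to one arm (Protocol Description and Participant Reporting) and send that arm its leaderboards (Leaderboard Distribution).
- **Allocation.** Section 6.1 uses a random number generator and opaque envelopes.

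No section mentions masking the sonographer, image reader or analyst, hiding the visit, or shuffling the images.

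**The concern.** De-identification and masking do different jobs. Separating the name from the number protects privacy. It does not stop someone who has worked with participant 012 for six weeks from knowing that person's arm, nor does it hide whether an image is from baseline or week 6. Opaque envelopes protect the assignment before it is made and have no bearing on readings made afterwards.

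The reading depends on where the reader places the fascial borders. A reader who knows arm and visit, and who expects one arm to improve more, can shift those placements without intending to. The questionnaires are self-reported by participants who know which programme they received, so they cannot be assessed blind. Reading a stored image can be. At stake is the credibility of the between-arm ultrasound comparison.

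**Working it through.** **1. The plan's own figures.** Section 12.2 gives 34 evaluable people (17 per group), 15% attrition and 40 in total. 34 / (1 − 0.15) = 40, and 17 / 0.85 = 20 per group. These reproduce and are not in dispute.

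**2. Is the reader masked?** Taking the provisions in turn:

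| Provision | What it hides | Group hidden from reader? | Visit hidden from reader? |
|---|---|---|---|
| Separate name file (7.1) | Name | Not stated | Not stated |
| One participant number throughout (17.2) | Name | Not stated; number constant across visits | Not stated |
| De-identified ultrasound measurements (17.4) | Name | Not stated | Not stated |
| Opaque envelopes (6.1) | Upcoming assignment | No | No |

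**3. Images involved.** The ultrasound procedure gives 5 exercises × (3 static + 3 starting) × 2 sides = 60 images per session.

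- All 40 people at both sessions: 40 × 60 × 2 = 4,800.
- 40 at baseline and 34 at week 6: 2,400 + 2,040 = 4,440.

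These counts show the size of the task, not the size of any bias.

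**4. Illustration of the effect.** Assumptions, none of them from the plan for this outcome: a two-sample t-test, two-sided alpha 0.05, no true difference, and a reading bias of *b* SD between arms. The .05 and the 17 per group are borrowed from section 12, where the sizing rests on research on home exercise and disability. Degrees of freedom = 17 + 17 − 2 = 32. Noncentrality = *b* × √(17/2) = 2.915 × *b*. The false-positive rate is the probability that a noncentral t exceeds the two-sided 5% limits.

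| Assumed bias (SD) | Noncentrality, 17 per group | Rate, 17 per group | Rate, 20 per group |
|---|---|---|---|
| 0 | 0 | 5.0% | 5.0% |
| 0.1 | 0.29 | 5.9% | 6.1% |
| 0.2 | 0.58 | 8.7% | 9.5% |
| 0.3 | 0.87 | 13.6% | 15.2% |
| 0.5 | 1.46 | 29.3% | 33.8% |

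**5. What the ratio absorbs.** Let S be the static reading and E the starting-position reading. If a reader inflates both by the same factor *k*, then kS / kE = S / E and the bias cancels. If the reader adds a constant *c* to both, (S + c) / (E + c) differs from S / E unless S = E. A bias in one position only passes straight through. The ratio therefore protects against one form of bias, not all.

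**The case against.** The case against is substantial, and several parts of it stand.

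- **Silence is not a statement.** A reader might infer that the image files show group and visit. The documents do not say so, and the participant number as described contains no group code. What can be said is that no masking is stated.
- **The reader is not named.** A reader might infer that the principal investigator measures the images. Sections 7.3, 19.1 and 25.1 make a team member likely, but section 25.1 also says members agreed designated roles, so a separate reader is not excluded.
- **Other outcomes.** A reader might infer that thickness is the only outcome not self-reported. That is not established. The Study Summary also lists onset of muscle activation, and the first and last exercise sessions take place in the laboratory with no statement of who times them.
- **The rates are hypothetical.** Section 17.1 gives no test or alpha for the ratio, and no reader error or SD appears anywhere. At 0.1 SD the inflation is under one percentage point. Because a common proportional bias cancels in the ratio, 0.3 to 0.5 SD is a strong assumption.
- **Baseline may be safer.** The documents do not say when the envelope is opened. Baseline images may be acquired before allocation is known, although they are still read later.
- **Reach is limited.** The outcome is secondary.

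None of this supplies the missing provision. The plan describes data or image handling in sections 7.1, 17.2 and 17.4 and does not mention masking in any of them.

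**Conclusion.** The concern holds as an unaddressed and avoidable risk of bias in a secondary outcome. Followed as written, the plan allows judgement-based readings, made under a directional hypothesis, by someone who may know the arm and the visit. It does not show that bias will occur.

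The size cannot be determined from the documents. Over an assumed bias of 0.1 to 0.5 SD with 17 per group, a nominal 5% rate would become 5.9% to 29.3%. This rests on a t-test that the plan does not specify and on the likely, but unstated, overlap between the image reader and the team delivering the programmes.

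A reader might extend the doubt to the trial's main conclusions. The documents do not support that: pain and disability come from questionnaires, and image reading does not touch them. The change should be made because it is cheap, not because the damage is known to be large. If masking is already intended, stating it in the protocol settles the point.

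**What to change.** Add to sections 7.1 and 17.1:

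1. Before measurement, image files are exported under random codes that hide participant number, group and session. The key records exercise, position and side so that the ratios can be built afterwards.
2. Images are measured in random order, after the last week-6 visit.
3. The key is held by another current team member, or in a locked script, and is linked to the readings only after the measurements are locked.

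**Cost.** A renaming script or a few hours of existing staff time, with no extra reader. Measurement has to wait until the week-6 images are complete. That fits section 9.1, which expects data collection within 4 months and primary analyses within 8 months of the start of enrolment.

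**What it does not fix.** At week 6 the operator knows the visit and may know the arm while placing the transducer and capturing images. Recoding stored files cannot undo that, so the report should list unmasked acquisition as a limitation.
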